10 DATA ANALYSIS/STATISTICAL METHODS

10.1 Sample Size

In this study, based on historical study data and study results of drugs of the same class and combined with clinical needs, a single-stage assessment method will be adopted to explore the efficacy of SHR-1210 combined with apatinib on ORR in ED-SCLC after failure of the first-line standard therapy.

Assume that in this study, the expected ORR in each treatment group of SHR-1210 + apatinib combination therapy is $\geq 30\%$ (alternative hypothesis), and that there is no need to continue the study if the ORR is $\leq 15\%$ (null hypothesis), at the significance level of 0.1 and a power of 80%, 40 subjects should be enrolled. If ≥ 9 (22.5%) of the 40 subjects have response, it can be considered that the ORR in this treatment group is 15% and the study drug is worthy of continued development.

With a dropout rate of 10% taken into account, each treatment group needs to enroll about 45 subjects. A total of 57 subjects are required in Stages I and II.

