10.5.2 Primary efficacy endpoint analysis

ORR is the primary efficacy endpoint of the study. It refers to the proportion of all enrolled subjects with CR or PR evaluated by RECIST v1.1. Response confirmation should be conducted for CR and PR. The point estimate of ORR and two-sided 95% confidence interval based on the Clopper-Pearson method will be calculated. The statistical analysis of ORR will be based on the FAS and ES, with FAS as the primary analysis set.

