2.3 Sample Size

In this study, based on historical study data and study results of drugs of the same class and combined with clinical needs, a single-stage assessment method will be adopted to explore the efficacy of SHR-1210 combined with apatinib on ORR in ED-SCLC after failure of the first-line standard therapy.

Assume that in this study, it is expected that the ORR in each treatment group of SHR-1210 + apatinib combination therapy is $\geq 30\%$ (alternative hypothesis), and assume that there is no need to continue the study if the ORR is $\leq 15\%$ (null hypothesis), at the significance level of 0.1 and a power of 80%, 40 subjects should be enrolled. If ≥ 9 (22.5%) of the 40 subjects have response, it can be considered that the ORR in this treatment group is 15% and the investigational drug is worthy of continued development.

With a dropout rate of 10% taken into account, each treatment group should enroll about 45 subjects, for a total of 135 subjects.

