3 STATISTICAL HYPOTHESIS

This study does not involve any statistical hypotheses and inference.

A single-stage assessment method will be adopted to explore the efficacy of SHR-1210 combined with apatinib on ORR in ED-SCLC after failure of the first-line standard therapy. The potential need for further development is indicated when the predefined number of responses (objective response) of a treatment group is reached (see Section 2.3 for details).

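### The go rule is worded as showing that the ORR equals 15%, the null value, and the only planned ORR interval (95%) is not matched to the 0.1 level of that rule

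*Protocol*

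**What the plan says.** Protocol 10.1 sets a null ORR of 15% or less, at which the study need not continue, and an alternative of 30% or more. The design statement is "at the significance level of 0.1 and a power of 80%, 40 subjects should be enrolled"; it does not say whether the level is one- or two-sided. The go rule is at least 9 responses (22.5%) in 40, and on meeting it "it can be considered that the ORR in this treatment group is 15% and the study drug is worthy of continued development". SAP 2.3 has the same conclusion: "it can be considered that the ORR in this treatment group is 15% and the investigational drug is worthy of continued development". The sample-size entry of the protocol synopsis repeats it.

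SAP 3 states: "This study does not involve any statistical hypotheses and inference". Protocol 10.3 carries the same sentence. Both sections then say that reaching the predefined number of responses indicates a potential need for further development, and refer back to the sample-size section for that number.

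For the analysis, Protocol 10.5.2 says that the point estimate and "two-sided 95% confidence interval based on the Clopper-Pearson method will be calculated", with the FAS as the primary set. The synopsis and SAP 5.4.1 also plan a 95% Clopper-Pearson interval. No other confidence level is planned, and no section makes the decision depend on where the interval lies.

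**The concern.** There are three linked faults.

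- **Wording.** The conclusion attached to success is the value that the sentence before it gives as the reason to stop. All three statements of the rule have this error, and no other section states the intended conclusion.
- **Status of the rule.** A null, an alternative, a significance level and a power are set, while Protocol 10.3 and SAP 3 deny any hypothesis or inference. A reader cannot tell what error rate the go decision is meant to carry.
- **Interval.** A 95% interval works at 0.025 per side. Just above the cut-off the report would show a go beside an interval that includes the uninteresting rate, with nothing in the plan to explain why.

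At stake is how the primary result is read when the count falls near the cut-off, which is likely even if the drug works as hoped.

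**Working it through.** **Inputs.** From Protocol 10.1 and SAP 2.3: null 15%, alternative 30%, level 0.1, power 80%, n = 40, go at 9 or more, 10% dropout leading to about 45. From Protocol 4: 6 Stage I subjects in the chosen group plus 39 in Stage II, which is 45. Assumption: the 0.1 is one-sided. The two-sided case is shown as well.

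**The plan's own figures.** With X binomial(40, p), the exact type I error is P(X ≥ r | 0.15) and the power is P(X ≥ r | 0.30).

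- r = 9 (as printed): type I error 0.135, power 0.889.
- r = 10: type I error 0.067, power 0.804.
- Dropout: 40 / 0.9 = 44.4, rounded up to 45, as stated.

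So n = 40 with level 0.1 and power 80% reproduces with a cut-off of 10, but not with the printed 9. If the 0.1 were two-sided (0.05 in the upper tail), the cut-off at n = 40 would be 11, with upper tail 0.030 and power only 0.691. The smallest exact design would then be n = 48 with 12 responses. The one-sided reading therefore fits n = 40 better, but the documents do not state it.

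**Link between interval and test.** The Clopper-Pearson lower limit L for x responses solves P(X ≥ x | n, L) = a. Here a = 0.025 for a 95% interval, 0.05 for 90% and 0.10 for 80%. Equivalently, L is the a-quantile of Beta(x, n − x + 1). The interval lies above 15% only when P(X ≥ x | n, 0.15) is below a.

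| n | x | P(X ≥ x), p = 0.15 | 95% lower | 90% lower | 80% lower |
|---|---|---|---|---|---|
| 40 | 9 | 0.135 | 10.8% | 12.3% | 14.1% |
| 40 | 10 | 0.067 | 12.7% | 14.2% | 16.2% |
| 40 | 11 | 0.030 | 14.6% | 16.3% | 18.3% |
| 40 | 12 | 0.012 | 16.6% | 18.3% | above 20% |
| 45 | 10 | 0.127 | 11.2% | 12.6% | 14.3% |
| 45 | 11 | 0.065 | 12.9% | 14.4% | 16.2% |
| 45 | 12 | 0.030 | 14.6% | 16.2% | 18.1% |
| 45 | 13 | 0.013 | 16.4% | 18.0% | 20.0% |

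The full 95% intervals at n = 40 are 10.8–38.5% (9), 12.7–41.2% (10), 14.6–43.9% (11) and 16.6–46.5% (12). At n = 40 the 95% interval clears 15% from 12 responses, the 90% interval from 11 and the 80% interval from 10. At n = 45 these counts are 13, 12 and 11.

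**How often it matters (n = 40, true ORR 30%).** P(X ≥ 9) = 0.889, P(X ≥ 10) = 0.804 and P(X ≥ 12) = 0.559.

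- 9 to 11 responses: 0.889 − 0.559 = 0.330.
- 10 or 11 responses: 0.804 − 0.559 = 0.245.

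The second figure is due only to the different error levels. The first adds the count of exactly 9, where the cut-off itself does not meet the one-sided 0.1 level.

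**The case against.** A reader might infer that the decision and the reported result contradict each other, and that this would happen in a quarter to a third of trials of an effective drug. The documents do not support that. The decision is a count (Protocol 10.3, SAP 3), the 95% interval is planned as an estimate, and no section requires it to exclude 15%. A screening rule at 0.1 and an interval at 0.025 per side are expected to differ near the cut-off. At 10 or 11 of 40 the overlap is only that difference, provided the 0.1 is one-sided.

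Four further objections deserve an answer.

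- The wording is probably a lost comparison sign, and no analysis depends on it. The intended meaning can be guessed, since the same sentence calls the drug worth developing. That limits the harm, but the stated conclusion of the decision rule is still wrong in three places.
- An added 80% interval does not settle everything: at 9 of 40 its lower limit is 14.1%. This stands. It shows that the printed cut-off does not meet the one-sided level of 0.1, so both need attention.
- The match between an 80% interval and the rule assumes a one-sided level. This stands. If the level is two-sided, the 90% interval is the matching one, and at 10 of 40 it still contains 15% (lower limit 14.2%).
- The no-hypotheses sentence can be read as disclaiming confirmatory inference. That is a fair reading, so it needs rewording rather than deletion.

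**Conclusion.** The point holds as a wording error and an unmatched interval. The statement that the ORR equals 15% on success is wrong as written in the synopsis, Protocol 10.1 and SAP 2.3. The planned 95% interval is not at the level of the go rule: it contains 15% at 9 to 11 of 40 and up to 12 of 45. With a true ORR of 30% and n = 40, 10 or 11 responses have probability 24%, and 9 to 11 have 33%. The claim of a contradiction between decision and result is not supported.

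The interval limits do not depend on the sidedness of the 0.1; the choice of matching interval does. The rule is given only for n = 40, whereas the FAS of the chosen group is planned at about 45, so the counts for 45 may be the ones that apply. The importance is minor: nothing in trial conduct changes, but the primary conclusion would be misread as the text stands.

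**What to change.** 1. In the synopsis, Protocol 10.1 and SAP 2.3, change the conclusion so that meeting the rule indicates an ORR greater than 15%.
2. State in the same places whether the significance level of 0.1 is one- or two-sided.
3. In Protocol 10.5.2 and SAP 5.4.1, keep the 95% interval and add the Clopper-Pearson interval at the design level for the number actually analysed: two-sided 80% if the level is one-sided, 90% if two-sided. Quote it with the go decision.
4. Reconcile the printed cut-off with the level. If one-sided, 10 of 40 gives type I error 0.067 and power 0.804; at n = 45, 11 responses are needed (0.065). If 9 of 40 is kept, state its error of 0.135 and power of 0.889.
5. In both Protocol 10.3 and SAP 3, reword the no-hypotheses sentence to say that there is no confirmatory inference beyond the go rule in Protocol 10.1 and SAP 2.3. Editing only one of them would leave the two documents inconsistent.

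The cost is a few sentences and one extra line of output. There is no effect on patients or data collection.

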5.5.1 Adverse events

Adverse events (AEs) will be analyzed based on the treatment-emergent adverse events (TEAEs):

- 1) All AEs that occur from the first study dose to 90 days after the last dose;
- 2) An AE that starts before the first study dose but worsens after administration.

Treatment-related AEs are defined as TEAEs with a causality of definitely related, possibly related, or indeterminable. If the relationship between an AE and the study drug is missing, the AE will be considered as a treatment-related AE.

All AEs will be coded with MedDRA 21.0. and graded by NCI-CTCAE v4.03. For the same SOC and/or PT, multiple cases of the same events that occur in one subject will be counted only once. For the same AE reported in one subject multiple times but varying in CTCAE grade, the AE of the greatest grade will be enumerated.

The incidence of AEs will be sorted from high to low based on their corresponding SOC in the SHR-1210 200 mg, IV, Q2W + apatinib 375 mg (or apatinib 250 mg), PO, QD group. The incidence of AEs in each SOC will be sorted from high to low based on their PT. If the incidences of \geq 2 PTs are equal, the AEs will be sorted alphabetically. If there is no AE under a SOC or PT, then analysis is not conducted.

The number of TEAE cases as well as the number of subjects based on the SS will be summarized in a table by dose group. The summary table should at least include the number of subjects with at least one TEAE/SAE/, TEAEs leading to treatment discontinuation, TEAEs leading to dose interruption or dose reduction, SAEs, SAEs leading to death, TEAEs of special interest, immune-related TEAEs (irAEs), and CTCAE grading. For all categories included in the summary table, CTCAE Grade ≥ 3 TEAEs and treatment-related AEs with an incidence of $\geq 5\%$ will be summarized by SOC and PT, respectively. Laboratory abnormalities with an incidence of $\geq 10\%$ will be summarized. TEAEs leading to treatment discontinuation, TEAEs leading to dose interruption or dose reduction, and all treatment-related AEs will be analyzed respectively for SHR-1210 and apatinib. An immune-related AE is determined in the case of an indeterminable immune-related AE.

In particular, the incidences and outcomes of AEs assessed per the CTCAE 4.03 below are separately analyzed:

- Hematologic toxicity
 - Grade 4, or
 - Grade ≥ 3 thrombocytopenia with hemorrhage, or
 - Grade ≥ 4 neutropenia with pyrexia and infection

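### The go rule of 9 responders in 40 has an exact one-sided error rate of 13.5% against the stated 10%, and no cut-off is given for a primary analysis set planned at up to 45

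*Protocol*

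**What the plan says.** Protocol 10.1 sets the null ORR at 15% and the alternative at 30%, and continues: "at the significance level of 0.1 and a power of 80%, 40 subjects should be enrolled". The decision rule is at least 9 ("22.5%) of the 40 subjects have response"). A 10% dropout allowance then raises the enrolment target: "each treatment group needs to enroll about 45 subjects". The synopsis and SAP 2.3 repeat the design and the cut-off. SAP 2.3 gives a different trial total, but the same 45 per group.

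Protocol 10.3 and SAP 3 make the efficacy signal a count. Further development is indicated "when the predefined number of responses (objective response) of a treatment group is reached", with a reference back to the sample size section. The same two sections say that the study involves no statistical hypotheses or inference.

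On the denominator, Protocol 10.5.2 says: "The statistical analysis of ORR will be based on the FAS and ES, with FAS as the primary analysis set". Protocol 10.4 and SAP 5.1.1 define the FAS by receipt of at least one dose. SAP 5.4.1 counts a missing response as not achieved, so a dosed dropout stays in the denominator. Protocol 4 plans 6 subjects per group in Stage I and 39 in Stage II.

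**The concern.** The number of responders is the only numerical efficacy criterion for taking the regimen forward, so its error rate should be the one printed beside it. The sample size section treats 40 as the number left after dropout. The primary analysis set does not remove dosed dropouts, so 40 is not the denominator that the plan leads to. A fixed count applied to a larger denominator is easier to reach by chance.

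With 45 subjects and 9 or 10 responders, one reader could call the result a go because 9 is the predefined number. Another could call it a no-go because fewer than 22.5% responded. The plan does not settle this before the data are seen.

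**Working it through.** **Inputs.** From Protocol 10.1: p0 = 0.15, p1 = 0.30, level 0.1, power 80%, n = 40, cut-off r = 9, dropout 10%. From Protocol 4: 6 + 39 = 45 in the selected group. The side of the test is not stated. I take it as one-sided, because the rule looks in one direction only.

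**Formulas.** False-go rate = P(X ≥ r), X ~ Binomial(n, 0.15). Power = P(X ≥ r), X ~ Binomial(n, 0.30).

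**Step 1: the plan's own figures.** The dropout step reproduces: 40 / 0.9 = 44.4, rounded up to 45. The error rate and power do not:

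- 9 of 40: false-go rate 13.5%, power 88.9%.
- 10 of 40: false-go rate 6.7%, power 80.4%. With 40 subjects, this is the cut-off that meets both 0.1 and 80%.

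The 9 may come from a normal approximation, 40 × 0.15 + 1.2816 × √(40 × 0.15 × 0.85) = 6 + 2.89 = 8.89, rounded up to 9. In exact terms, a cut-off of 9 first meets both targets at n = 37 (error 9.2%, power 82.4%).

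**Step 2: other FAS sizes.**

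| FAS size | False-go rate, r = 9 | Smallest r with exact error ≤ 0.1 | False-go rate at that r | Power at that r |
|---|---|---|---|---|
| 39 | 12.0% | 10 | 5.8% | 77.6% |
| 40 | 13.5% | 10 | 6.7% | 80.4% |
| 41 | 15.2% | 10 | 7.7% | 83.0% |
| 42 | 16.9% | 10 | 8.9% | 85.2% |
| 43 | 18.7% | 11 | 4.9% | 78.5% |
| 44 | 20.6% | 11 | 5.7% | 81.1% |
| 45 | 22.5% | 11 | 6.5% | 83.5% |

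At n = 43 a cut-off of 10 just misses, at 10.06%. The 22.5% in the last row is an error probability; its match with 9/40 = 22.5% in the protocol is a coincidence.

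**Step 3: dropouts as non-responders.** Suppose, as an assumption, that 10% of a FAS of 45 are dosed dropouts who cannot respond. The rates become 0.9 × 0.15 = 0.135 and 0.9 × 0.30 = 0.27. For n = 45:

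- r = 9: false-go rate 14.5%, power 89.3%.
- r = 10: false-go rate 7.4%, power 81.2%.
- r = 11: false-go rate 3.4%, power 70.4%.

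**Step 4: the cut-off read as a proportion.** At least 22.5% of the FAS means 9 responders at n = 39 and 40, 10 at n = 41 to 44, and 11 at n = 45. The false-go rate is then 12.0%, 13.5%, 7.7%, 8.9%, 10.06%, 11.4% and 6.5%, which is above 0.1 at four of the seven sizes.

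**The case against.** Several points on the other side stand.

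- A reader might infer that moving from 40 to 45 subjects raises the error from 10% to 22.5%. It does not. The rule is already at 13.5% with 40, so 3.5 of the 12.5 points come from the cut-off and about 9 from the denominator. Analysing exactly 40 subjects would not restore 10%.
- The 22.5% is an upper end. Undosed subjects leave the FAS, and dosed dropouts without a response lower the achievable rate, as Step 3 shows.
- Nothing in either document applies 9 to 45 subjects. Read as a proportion, the rule would require 11 of 45, with an error of 6.5%. What can be shown is that the cut-off is undefined at that size.
- The count is not the only condition for a go. Protocol 4 also requires acceptable safety, and a go signals only a potential need for further development.
- Both documents disclaim hypotheses and inference. That softens the consequence, but the same sections use the count as the efficacy signal, and 10.1 attaches a level and a power to it.

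A reader might also take the SAP 5.5.1 label "or apatinib 250 mg), PO, QD group" as evidence of a planned 250 mg group, which would leave only 39 subjects on the chosen regimen. That text sets the sort order of adverse event tables, and elsewhere 250 mg appears as the reduced level for individual subjects (Protocol 6.4.2). It does not establish such a group. The fact that 6 + 39 equals the per-group 45 suggests that pooling Stage I is intended. Even so, Protocol 4 leaves the Stage II schedule and apatinib dose to be chosen after Stage I, and no rule says who counts if they differ.

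**Conclusion.** Wrong as written, on two counts. The stated 0.1 does not belong to 9 of 40, whose exact one-sided error is 13.5%. The cut-off is also missing for the FAS sizes that the plan would produce. Keeping 9 gives a false-go rate of 13.5% at n = 40, rising to at most 22.5% at n = 45, and about 14.5% at n = 45 under the 10% dropout assumption. It exceeds 0.1 at every size from 39 to 45.

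This rests on a one-sided level, on 15% and 30% as the true confirmed response rates, and, for the larger sizes, on pooling Stage I with Stage II. The documents do not support the stronger claim that the trial will run at 22.5%.

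**What to change.** In Protocol 10.1, the synopsis and SAP 2.3:

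1. State that the 0.1 level is one-sided.
2. Define the cut-off as the smallest count with exact error at most 0.1 at the actual FAS size: 10 for 39 to 42, 11 for 43 to 45. If extra Stage I subjects are added, as Protocol 7.1.1 allows, the same definition gives 11 for 46 to 48.
3. Print the power at each size from the table, including the two below 80% (77.6% at 39, 78.5% at 43). Say that it is lower if dropouts count as non-responders: about 70% for 11 of 45 under the 10% assumption. State whether 15% and 30% refer to all FAS subjects or to those who do not drop out.
4. State whether Stage I subjects count toward the go rule if the Stage II regimen or dose differs from theirs, and reconcile Protocol 4, Protocol 10.1 and SAP 5.5.1 on this. That is a counting rule only; the choice of regimen or dose is outside this point.

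The cost is wording. One or two more responders are needed than under a cut-off of 9, and power falls, from 88.9% to 80.4% at n = 40 and from 95.3% to 83.5% at n = 45. No patients are added. The change should be made before any response data are reviewed, and in any case before database lock.

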10.2 Statistical Analysis Plan

Detailed summaries and methods of statistical analyses for the data collected from the study will be included in the statistical analysis plan (SAP), which will be finalized and filed by the sponsor. The SAP should be revised accordingly if there are any changes to the study protocol that may have an obvious impact on the SAP, as determined by the sponsors or principal investigators. The SAP must be finalized before database locking.

10.3 Statistical Hypotheses

This study does not involve any statistical hypotheses and inference.

A single-stage assessment method will be adopted to explore the efficacy of SHR-1210 combined with apatinib on ORR in ED-SCLC after failure of the first-line standard therapy. The potential need for further development is indicated when the predefined number of responses (objective response) of a treatment group is reached (see Section 10.1 for details).

10.4 Analysis Sets

The analysis sets in this study include:

Full analysis set (FAS): an analysis set determined based on the intent-to-treat principle. This analysis set includes all subjects who have been randomized and have received at least one dose of the study drug. In the FAS-based analysis, subjects will be analyzed by groups after randomization (regardless of the actual treatment they receive).

Per-protocol set (PPS): a subset of the FAS. Subjects with protocol violations that are judged to have a significant effect on the efficacy will be excluded from this set. The list of subjects included into or excluded from the PPS should be reviewed and determined by the sponsor and the investigator before the database is locked.

Evaluable set (ES): a subset of the FAS, defined as the all enrolled subjects receive at least one dose of the study drugs and receive post-baseline tumor assessment at least once.

Safety set (SS): All subjects who have been randomized and have received at least one dose of the study drug. Analyses based on the safety set will be carried out according to the actual treatment received by the subjects.

ADA set (ADAS): All enrolled subjects who have received at least one dose of the study drug and have baseline and at least one post-baseline ADA evaluation data.

Tumor biomarkers set (TMKS): Subjects who have been randomized and received at least one dose of the study drugs, and have tumor biopsy samples make up the PD-L1 or TMB set.

10.5 Statistical Methods

10.5.1 Basic methods

Unless otherwise specified, standard descriptive statistics will be summarized by different type of variables:

- Continuous data will be summarized using mean, standard deviation, median, maximum, and minimum;
- Categorical data will be summarized using frequency and percentage;
- For time-to-event data, Kaplan-Meier method will be used to estimate the survival function and median time to event onset, and a survival curve will be plotted.

The baseline is generally defined as the last pre-administration observation before the first dose (including the very day).

